Study Participants	Women who have completed primary treatment for endometrial cancer within 36 months; no evidence of recurrence; able to provide consent; able to participate in English-language group sessions.	
Sample Size	Estimated 30 participants.	
Follow up duration	Follow up: 12 months	
Planned Study Period	February 2026 – January 2028	
	Objectives	End Points / Outcome Measures
Primary	
Is the OurPERSPECTIVE course acceptable and useful for women who have completed treatment for endometrial cancer?
	
The primary outcome is the acceptability and feasibility of the OurPERSPECTIVE survivorship course.
 
This will be assessed using:
 
 – Recruitment rates (proportion of eligible women approached who consent to take part). – Retention rates (proportion of participants completing the 8-week course). – Attendance and engagement (number of sessions attended). – Participant evaluation of the course (questionnaire ratings of usefulness and relevance, and qualitative feedback from focus groups). 
These measures will determine whether the intervention and study procedures are acceptable and feasible, and whether

SPONSOR REFERENCE: 1097

OurPERSPECTIVE endometrial cancer survivorship Study

Protocol Version v1.0 14/10/2025

IRAS: 363748

		progression to a full randomised controlled trial is justified.
Secondary	
 – Can we recruit and retain women to take part in the OurPERSPECTIVE course? – Do women complete the questionnaires and engage with feedback assessments? – What changes or improvements to the course content or delivery are suggested by participants? 	
Secondary outcomes will focus on exploratory measures to inform the design of the subsequent randomised controlled trial. These include:
 
 – Recruitment feasibility, such as reasons for declining participation and the characteristics of those recruited versus not recruited. – Questionnaire completion rates and data quality, to assess the practicality of collecting patient-reported outcomes in this population. – Changes in patient-reported outcomes over the course of the study, including quality of life, wellbeing, and fear of recurrence, measured using validated questionnaires (e.g. SF-36, HADS, EQ-5D-5L). – Participant preferences regarding delivery mode (virtual group versus other formats) and suggestions for improvement. – Qualitative feedback on barriers and facilitators to participation, acceptability of study materials, and relevance of course content. 
These outcomes will provide information on which measures are most suitable and acceptable for inclusion in the future definitive RCT.

[figure not shown]
SPONSOR REFERENCE: 1097

OurPERSPECTIVE endometrial cancer survivorship Study

Protocol Version v1.0 14/10/2025

IRAS: 363748

STUDY FLOW CHART

SPONSOR REFERENCE: 1097
OurPERSPECTIVE endometrial cancer survivorship Study

Protocol Version v1.0 14/10/2025

IRAS: 363748

LIST OF ABBREVIATIONS

AE	Adverse Event
AR	Adverse Reaction
CI	Chief Investigator
CRF	Case Report Form
CTU	Clinical Trials Unit
GCP	Good Clinical Practice
ICF	Informed Consent Form
ISF	Investigator Site File
NHS R&D	National Health Service Research & Development
PI	Principal Investigator
PIC	Participant Identification Centre
PIS	Participant Information Sheet
QC	Quality Control
RCT	Randomised Control Trial
REC	Research Ethics Committee
SAE	Serious Adverse Event
SAR	Serious Adverse Reaction
SOP	Standard Operating Procedure
TMF	Trial Master File
TMG	Trial Management Group
TSC	Trial Steering Committee

KEY WORDS

Feasibility study; endometrial cancer; survivorship intervention; patient education.

SPONSOR REFERENCE: 1097

OurPERSPECTIVE endometrial cancer survivorship Study

Protocol Version v1.0 14/10/2025

IRAS: 363748

PROTOCOL AMENDMENT HISTORY

Amendment Reference	Protocol version no.	Protocol Date	Author(s) of changes	Summary of changes made
				.

SPONSOR REFERENCE: 1097

OurPERSPECTIVE endometrial cancer survivorship Study

Protocol Version v1.0 14/10/2025

IRAS: 363748

1 Background and Rationale

Endometrial cancer is the most common gynaecological malignancy in high-income countries, and incidence is rising, largely due to obesity alongside population ageing and metabolic risk factors [1]. Although overall survival is favourable for many, women frequently report persistent problems after treatment, including fatigue, bladder and bowel dysfunction, sexual difficulties, sleep disturbance, and fear of recurrence; these symptoms reduce quality of life and are common in endometrial cancer survivorship [2–4]. Such sequelae are often under-recognised and under-addressed in routine follow-up [5].

Cancer survivorship refers to the phase beyond initial treatment and includes the physical, psychological, social, and functional consequences of cancer and its management, with a focus on living well with and beyond cancer and addressing late and long-term effects [6,7,8]. Survivorship courses are structured educational programmes to support this phase.

Current survivorship interventions for gynaecological cancers remain limited and are rarely co-designed with patients. Evidence from oncology indicates that group-based, peer-supported programmes can improve psychological wellbeing, self-efficacy, and quality of life [9, 10]. However, such approaches have not been systematically adapted or tested for women with endometrial cancer in the UK NHS context, despite documented unmet needs in gynaecological cancer survivorship [11]. Additionally, survivorship support shows inequitable reach, with ethnic minority groups and people living in socio-economic deprivation reporting poorer experience and access to cancer care, underscoring the importance of equitable design and delivery [12,13].

The OurPERSPECTIVE course was co-designed with women living after endometrial cancer and healthcare professionals to address these gaps. It is an 8-week structured, group-based intervention focused on physical, psychological, and lifestyle challenges after treatment. This feasibility study will establish whether recruitment, retention, delivery, and evaluation are practicable within the NHS, informing a future definitive trial.

2 Objectives and Outcome Measures/Endpoints

Objectives	Outcome Measures/Endpoints	Timepoint(s) of evaluation of this outcome measure
Primary Objective, Outcome, Timepoint(s)		

Is the OurPERSPECTIVE course acceptable and useful for women who have completed treatment for endometrial cancer?
	
The primary outcome is the acceptability and feasibility of the OurPERSPECTIVE survivorship course.
 
This will be primarily assessed using:
 
 – Retention rates (proportion of participants completing the 8-week course). – Recruitment rates (proportion of eligible women approached who consent to take part). 
These measures will determine whether the intervention and study procedures are acceptable and feasible.
	
Data will be collected in three stages:
 
Before the trial begins to collect baseline participant data.
 
Participants will be asked to keep a diary of their experiences and views of the course and the different modules
 
At week 4 of the 8-week intervention, representing mid-point data, with short interviews with individuals to assess usability and engagement with the intervention.
 
Follow up period after the 8-week intervention at 3-months, 6-months and 12-months post-intervention.

Secondary Objective(s), Outcome(s), Timepoint(s)		

1. Can we recruit and retain women to take part in the OurPERSPECTIVE course within the NHS?
 
2. Do women complete the questionnaires and give feedback as expected?
 
3. What changes or improvements to the course content or delivery are suggested by participants?
	
Secondary outcomes will focus on exploratory measures to inform the design of the subsequent randomised controlled trial. These include:
 
 – Recruitment feasibility, such as reasons for declining participation and the characteristics of those recruited versus not recruited. – Attendance and engagement (number of sessions attended). – Participant evaluation of the course (questionnaire ratings of usefulness and relevance, and 	
Data will be collected in three stages:
 
Before the trial begins to collect baseline participant data.
 
Participant diaries
 
At week 4 of the 8-week intervention, representing mid-point data, with short interviews with individuals to assess usability and engagement with the intervention.
 
Follow up period after the 8-week intervention at 3-months,

SPONSOR REFERENCE: 1097

OurPERSPECTIVE endometrial cancer survivorship Study

Protocol Version v1.0 14/10/2025

IRAS: 363748

Objectives	Outcome Measures/Endpoints	Timepoint(s) of evaluation of this outcome measure
	
qualitative feedback from focus groups).
 
 – Questionnaire completion rates and data quality, to assess the practicality of collecting patient-reported outcomes in this population. – Changes in patient-reported outcomes over the course of the study, including quality of life, wellbeing, and fear of recurrence, measured using validated questionnaires (e.g. SF-36, HADS, EQ-5D-5L). – Participant preferences regarding delivery mode (virtual group versus other formats) and suggestions for improvement. – Qualitative feedback on barriers and facilitators to participation, acceptability of study materials, and relevance of course content. – Assessing how equity characteristics (PROGRESS-Plus) determine engagement and usability of the intervention. 
These outcomes will provide information on which measures are most suitable and acceptable for inclusion in the future definitive RCT.
	6-months and 12-months post-intervention.
Exploratory Objective(s) Outcome(s), Timepoint(s)		
N/A	N/A	N/A

3 Study Design

This is a single-centre feasibility study based at the University Hospitals of Leicester NHS Trust. The study will recruit women who have recently completed treatment for endometrial cancer through NHS secondary care at University Hospitals of Leicester NHS Trust. The intervention, OurPERSPECTIVE, is delivered virtually as an online group course facilitated by a gynaecology nurse specialist: the structure of the module will follow the example showed in figure 2. The content of each module is summarised in figure 3. The online course will be complemented with an interactive workbook which will be supplied to participants.

All study activities (identification, recruitment, consent, delivery of the intervention, and follow-up) will be managed through this single NHS hospital site. No other types of sites (e.g. GP practices or community venues) are involved. There are no participant identification centres; recruitment will be undertaken directly by the clinical care team at Leicester Cancer Centre.

Figure 2: Structure of a module within the OurPERSPECTIVE Course.

Figure 3: Topics for discussion in the OurPERSPECTIVE Modules.

4 Participant Eligibility Criteria

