5.4 Study assessments

Demographic and Clinical Data

Demographic information (age, sex, ethnicity, postcode) and relevant clinical details (date of completion of primary treatment, cancer and stage, and current disease status) will be obtained from routine NHS clinical records at the University Hospitals of Leicester NHS Trust. Specifically, the following information will be sought:

Anthropometric Data: Height and weight will be measured and used to calculate Body Mass Index (BMI).

SPONSOR REFERENCE: 1097

OurPERSPECTIVE endometrial cancer survivorship Study

Protocol Version v1.0 14/10/2025

IRAS: 363748

Endometrial Cancer Data: Information will be collected on recurrence, definitive treatment undertaken, menopause status.

Medical History Data: Information on other medical conditions/medications will be collected, as well as smoking and alcohol intake questions.

Equity characteristics (modified PROGRESS-Plus): Information on equity characteristics and social circumstance will be collected, with the option of 'prefer not to say' provided for information deemed to be of a sensitive nature.

Baseline Questionnaires (Week 0)

At enrolment, participants will complete self-reported questionnaires delivered electronically or on paper (depending on participant preference). These will include:

- Quality of life: SF-36
- Psychological wellbeing: Hospital Anxiety and Depression Scale (HADS)
- Multi-dimensional health-related quality of life assessment: EQ-5D-5L
- Acceptability and usability questions tailored to the intervention

Midpoint Interview (Week 4)

At week 4, selected participants will be invited to take part in a short telephone interview to assess the feasibility and acceptability during the intervention. This will be with the research fellow. The interview will be recorded using Microsoft Teams.

Post-Intervention Questionnaires (3 months)

After completing the OurPERSPECTIVE course, participants will be asked to complete the same set of questionnaires as at baseline to assess feasibility of data collection and exploratory changes in quality of life, psychological wellbeing, and fear of recurrence. It is anticipated that this data collection will be approximately 3-months since recruitment. Additional acceptability and usability questions will capture participant feedback on the intervention as a whole. Further follow up questionnaires will be sent at the 6-month and 12-month point, respectively.

OurPERSPECTIVE Course Attendance

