5.4.1 Long term follow-up assessments

This is a feasibility study and long-term follow-up beyond the 8-week intervention period includes the 3-month, 6-month and 12-month questionnaires to investigate the longer-term impact of the course.

Frequency and duration of follow-up

Participants will be sent questionnaires approximately 2 weeks after completion of the 8-week OurPERSPECTIVE course (3 month); and will be invited to participate in focus group or interviews to approximately 4 weeks after completing of intervention completion. Further long-term follow up will be completed at 6-month and 12-month of intervention completion with the included questionnaires to compare to baseline symptom burden.

Assessments

Post-intervention assessments will include the same questionnaires completed at baseline (SF-36, HADS, EQ-5D-5L, acceptability/usability questions) and an optional focus group.

SPONSOR REFERENCE: 1097

OurPERSPECTIVE endometrial cancer survivorship Study

Protocol Version v1.0 14/10/2025

IRAS: 363748

These measures will capture short-term changes in wellbeing and evaluate the acceptability of the intervention.

Differences from standard care

The course and the assessments are additional to standard NHS follow-up, which typically focuses on clinical surveillance for recurrence and does not include a structured survivorship course, questionnaires or peer-support evaluation.

Retention strategies

Retention will be supported through flexible scheduling of questionnaires (online or postal completion), reminder emails/telephone calls, and provision of modest shopping vouchers as a token of thanks. The focus on short-term follow-up reduces risk of attrition.

Identification of lost to follow-up

Participants will be considered lost to follow-up if they do not return post-intervention questionnaires and cannot be contacted after three attempts (e.g. email, phone, postal reminder).

Handling missed data

If questionnaire time-points are missed, participants will still be invited to complete subsequent assessments where possible. Early-exit data will be recorded if participants withdraw before completing the study.

Data from non-adherers

For participants who discontinue the intervention but do not withdraw consent, available outcome data (e.g. questionnaires completed up to that point) will still be retained and included in feasibility analysis.

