8.3.3 Secondary outcome analysis

Secondary outcomes will assess change in participant-reported quality of life and psychological well-being. Data will be collected using the SF-36, Hospital Anxiety and Depression Scale (HADS), and EQ-5D-5L at baseline, post-intervention, and 3-, 6- and 12-month follow-ups. Descriptive statistics will summarise scores at each timepoint. Mean within-participant changes from baseline will be presented with 95 % confidence intervals and standardised effect estimates.

Qualitative data from midpoint interviews (week 4) and the post-intervention focus groups/interviews will also be analysed using Reflexive Thematic Analysis.

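### Change in fear of recurrence is a stated questionnaire outcome, but the protocol assigns no questionnaire to it and the analysis section omits it

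*Protocol*

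**What the plan says.** **The outcome.** The Study Summary and the objectives table in Section 2 both include, among the secondary outcomes, change over the study in "quality of life, wellbeing, and fear of recurrence, measured using validated questionnaires (e.g. SF-36, HADS, EQ-5D-5L"). Section 5.4, under the post-intervention questionnaires, says that repeating the baseline set will serve to assess "exploratory changes in quality of life, psychological wellbeing, and fear of recurrence".

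**The instruments.** Section 5.4 lists four baseline components, each with its purpose:
- The SF-36 is given to quality of life.
- The HADS is entered as "Psychological wellbeing: Hospital Anxiety and Depression Scale (HADS)".
- The EQ-5D-5L is entered as "Multi-dimensional health-related quality of life assessment: EQ-5D-5L".
- The fourth component is a set of course-specific items on acceptability and usability.

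Section 5.4.1 says that the post-intervention assessments comprise "the same questionnaires completed at baseline (SF-36, HADS, EQ-5D-5L, acceptability/usability questions)", with an optional focus group. Section 8.3.1 names EQ-5D-5L, HADS and SF-36 as the baseline questionnaires.

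**The analysis.** Section 8.3.3 opens: "Secondary outcomes will assess change in participant-reported quality of life and psychological well-being". It names SF-36, HADS and EQ-5D-5L as the data sources and does not mention fear of recurrence.

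**The concern.** The protocol treats fear of recurrence as a construct of its own, listed beside quality of life and wellbeing, and says that a validated questionnaire will measure it. It then fixes a questionnaire set in which nothing is given that role, and an analysis section from which the construct has gone.

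Two things are at stake. First, a stated outcome would have no planned quantitative result, and the final report would have to leave it out or explain its absence. Second, Section 2 says that the secondary outcomes are there to show which measures are suitable and acceptable for the definitive trial, and it lists questionnaire completion and data quality among them. A scale that is never given yields no information of that kind. The topic is not incidental to the study: Section 1 names it among the persistent problems after treatment, and Section 5.5.1 lists it as a course module.

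Timing matters because a baseline value cannot be recovered once a woman has started the course.

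**Working it through.** There is no figure to reproduce. The sample size in Section 8.1 is pragmatic, with no error rate, power, effect size or standard deviation. The check sets every list of outcomes against every list of instruments.

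**Where fear of recurrence is promised**

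| Place | Listed as an outcome? | Instrument assigned to it |
|---|---|---|
| Study Summary | Yes, by validated questionnaire | None; three examples given for all constructs together |
| Section 2 | Yes, by validated questionnaire | None; same three examples |
| Section 5.4, post-intervention questionnaires | Yes | None; refers back to the baseline set |
| Section 8.3.3 | No | None |

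**What the questionnaire set contains**

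| Place | Instruments named | Wording open or closed? |
|---|---|---|
| Study Summary, Section 2 | SF-36, HADS, EQ-5D-5L | Open (introduced by e.g.) |
| Section 5.4, baseline | The three, plus acceptability and usability questions | Partly open (said to be included) |
| Section 5.4.1 | The same four components | Ties follow-up to the baseline set |
| Section 8.3.1 | EQ-5D-5L, HADS, SF-36 | Closed |
| Section 8.3.3 | SF-36, HADS, EQ-5D-5L | Closed |

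**Construct by construct, using the assignments in Section 5.4**
- Quality of life: 2 instruments (SF-36, EQ-5D-5L).
- Psychological wellbeing: 1 instrument (HADS).
- Fear of recurrence: 0 instruments.

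The argument does not depend on the item content of the three questionnaires, which the protocol does not show. It depends on the protocol's own assignment. Section 5.4 gives HADS to psychological wellbeing, and the same section lists fear of recurrence separately from psychological wellbeing, so the protocol does not offer HADS as its measure of fear of recurrence.

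**Size.** One of three named constructs has no instrument. With about 30 participants (Section 8.1), the number of validated baseline-to-follow-up pairs for that construct is 0 of about 30. Section 5.5.1 plans 3 cohorts of 10. If a scale were added only after a cohort had started, the baseline of that cohort would be lost: 10 / 30, or one third of the possible change data per cohort.

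**The case against.** **The list may be open.** The outcome tables use e.g., and Section 5.4 says what the questionnaires will include. On those words alone, a further scale could be intended. This has some force for Sections 5.4 and 5.4.1, but Sections 8.3.1 and 8.3.3 name the three instruments without qualification, and no fear-of-recurrence scale is named anywhere in the protocol.

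**It may be left to a statistical analysis plan.** An analysis plan can define how collected data are analysed. It cannot supply an instrument that the protocol does not give to participants.

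**Other sources may cover it.** This stands in part. Participants keep a diary on the modules, of which fear of recurrence is one. Selected women are interviewed at week 4, and focus groups follow the course. The tailored acceptability and usability questions have content that the protocol does not show. A reader might infer that the study would learn nothing about fear of recurrence; the documents do not support that. But the diary, interviews and focus groups provide no pre-course baseline, and none of these sources, the tailored questions included, is described as a validated fear-of-recurrence scale.

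**The consequence is small.** This largely stands. The primary outcomes concern feasibility and acceptability, Section 8.3.2 plans no formal hypothesis testing, and none of the three secondary objectives in Section 2 depends on a fear-of-recurrence score. What remains is the loss of one stated exploratory outcome and of any piloting of such a scale.

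**Stronger readings that the text does not carry.** A reader might infer that fear of recurrence is the likely outcome of the definitive trial, or the outcome closest to the intervention. The protocol does not name that trial's outcome. Fear of recurrence is one entry among eight in the module list of Section 5.5.1 and one of several problems in Section 1, with no ranking. A reader might also expect the HADS anxiety score to be reported as a stand-in, but nothing in the protocol proposes that.

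**Conclusion.** The mismatch is real and rests on the protocol's text alone. Change in fear of recurrence is promised in three places as a questionnaire outcome, no questionnaire is assigned to it, and the secondary analysis leaves it out. Followed as written, the plan gives no validated change score for this outcome and no completion or data-quality information on a scale for it. Qualitative comments may still be available.

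The conclusion assumes that the set in Sections 8.3.1 and 8.3.3 is the set that will be used. If a scale is already intended, the gap is one of documentation, and naming the scale closes it.

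The weight is moderate: one exploratory secondary outcome in a feasibility study of about 30 women. It should be settled before the first baseline questionnaire.

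**What to change.** Either of two changes resolves the contradiction; the choice is the sponsor's.

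1. **Measure it.** Choose one short validated fear-of-recurrence scale and give it at baseline and at each questionnaire follow-up. Name it in the Study Summary and in Sections 2, 5.4, 5.4.1, 8.3.1 and 8.3.3, and add fear of recurrence to the outcomes analysed in Section 8.3.3. The cost is a few minutes per woman at each timepoint (an estimate, since it depends on the scale) and possibly a licence. Section 13.1 says that questionnaire licences will be covered from a research fund, but does not show whether an additional one has been allowed for.

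2. **Withdraw it as a questionnaire outcome.** Remove fear of recurrence from the questionnaire-based outcomes in the Study Summary, Section 2 and Section 5.4, and state that it is explored qualitatively only, through the diaries, interviews and focus groups. This costs only text, but no such scale would then be piloted for the later trial.
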